- We should avoid interim analyses and unnecessary "alpha-spending," which reduces the power of the study.
- Study participants in both treatment groups are being provided with beneficial interventions.

The Safety Officer may request an interim analysis at any time during the study for purposes of assessing safety/harm.

The study will be terminated if there is clear evidence of harm or harmful side-effects of the treatment or participation in the study that outweighs evidence of the benefits of participation. Each Safety Officer report (approximately every six months) will conclude with a recommendation to continue or to terminate the study. A copy of this letter will be forwarded to the IRB and the NIH Program Officer. A termination recommendation may be made by the Safety Officer at any time during the study if deemed necessary.

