Serious Adverse Events (medical problems where the study participant was hospitalized, had any problem resulting in a persistent or significant disability, had any problems that were life-threatening, or resulted in a birth defect in a newborn child) will be assessed at 3 and 6 months. Adverse events (any medical illnesses or injuries requiring a visit to a medical care provider or institution) that the participant believes possibly related to their participation in the study will be assessed as part of the follow-up assessments at 3 and 6 months. A report form has been designed for this purpose to at least include a brief description, severity, resolution, potential relationship to study participation, and actions taken with respect to study participation. The PI will evaluate each event to determine if it meets the criteria of an Unanticipated Problem (UP) – which is unexpected, possibly related to participation in the study, and harmful. We will inform the IRB immediately of all Unanticipated Problems, and all adverse events, regardless of seriousness, will be reported to the IRB during annual reports/reviews.

Some also express concern that obesity treatment can increase the risk of unhealthful eating behaviors, although the bulk of available data do not support this, including a recent meta-analysis. Since the 1980's, our research group has studied risk and prevention of disordered eating behaviors among children and teens. As a result, we carefully consider the risks of disordered eating behaviors in all our obesity prevention and treatment research. A diagnosis of anorexia nervosa, bulimia nervosa or binge eating disorder, past or present, and any self-induced vomiting, or use of diuretics or laxatives for weight loss are exclusions for the study for the adult participant and any child living in the household.

The wise social psychological interventions proposed in this research have been found to be beneficial in multiple past studies in other domains (e.g., schools) and are designed to bolster self-integrity and focus on overall well-being, not specifically on weight.

d. Stanford Populations

We will not recruit from Stanford laboratory personnel, employees, or students.

e. Healthy Volunteers

Participants are children with obesity who are otherwise healthy and their parents/guardians who are also healthy.

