- Live in continental USA.
- Internet access and Zoom video capability.
- Interest in receiving Stanford online activities.

Completion of baseline data collection activities, including willingness to use the Stanford provided electronic scale and tape measure to measure weight and height during the assessment sessions.

As we are interested in testing generalizable strategies for weight control in diverse populations, the eligibility criteria are designed to be liberal, to maximize the generalizability of the results, but also maintain the internal validity of the test of the intervention.

ii. Exclusion Criteria

To enhance internal validity, children will not be eligible if they:

1) Diagnosed with a medical condition affecting growth (a genetic or metabolic disease/syndrome associated obesity, Type 1 diabetes, Type 2 diabetes taking medication, chronic gastrointestinal diseases, Chronic renal diseases, uncorrected structural heart disease, heart failure, heart transplant, AIDS or HIV infection, pregnancy); are taking medications affecting growth (systemic corticosteroids more than 2 weeks in the past year, insulin, oral hypoglycemics, thyroid hormone, growth hormone);

2) Child has had, or in next 6 months plans to have bariatric surgery;

3) Parent/guardian, or any child in the household has ever been diagnosed with an eating disorder such as anorexia nervosa, bulimia nervosa or binge eating disorder, or self-induce vomits or uses diuretics or laxatives for weight loss.

4) Child cannot fully participate in the interventions (e.g. be able to participate in routine physical activity)

5) Cannot fully participate in the assessments: child or primary caregiver not able to read surveys in English or Spanish, child not in mainstream classes at least 70%

h. Screening Procedures

On our study website, a link to an online screener in REDCap will be available. We will obtain a limited waiver of authorization for recruitment prior to asking potential participants to complete the online screener. (Section 15). After completing the waiver of documentation, the screening survey will assess inclusion and exclusion criteria listed above.

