Adverse events (any medical illnesses or injuries requiring a visit to a medical care provider or institution) will be assessed as part of the follow-up assessments. An adverse events recording form has been designed for this purpose, to systematically document all adverse events occurring during the course of the study (to at least include a brief description, severity, resolution, potential relationship to study participation, and action taken with respect to study participation). Intervention staff will also be trained to investigate and record adverse events continuously, between assessments, as they become aware of them.

Although the evidence suggests treatment does not cause disordered eating, overweight children and families seeking treatment are at increased risk irrespective of participating in treatment. Therefore, as noted above, diagnosis of anorexia nervosa, bulimia nervosa or binge eating disorder, past or present, as well as self-induced vomiting and use of diuretics or laxatives for weight loss are exclusions for the study for both children and parents.

A Safety Officer and the Stanford University Administrative Panel on Human Subjects in Medical Research (IRB) will be informed within 7 days of learning of all unanticipated

problems. With the exception of SAEs for otherwise healthy childbirth, all adverse events, regardless of seriousness, will be reported to the IRB during annual reports/reviews.

The Safety Officer is an independent physician who is designated to provide ongoing oversight to protect participant safety and make ongoing assessments of the balance between risks and benefits. The Safety Officer is a Stanford University faculty member who is not involved in this study or in the Principal Investigator's chain of command. They have relevant clinical and clinical trials experience and expertise. Confidentiality of participant data will be maintained throughout all Safety Officer reviews. The Safety Officer will act in an advisory capacity to NIH, the Principal Investigator, and Stanford University to monitor patient safety and the performance of the study.

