Throughout the course of the study, while participants are enrolled, the Safety Officer will meet with the Principal Investigator to review study progress and safety, including all adverse events. An emergency meeting may be called at any time by the Principal Investigator, the Safety Officer or the study Statistician, should questions of participant safety arise. At meetings during the course of the trial, the Safety Officer's responsibilities are to:

- review plans for data safety and monitoring;
- evaluate the progress of the trial, including periodic assessments of data quality and timeliness, participant recruitment, accrual and retention, participant risk versus benefit, and other factors that can affect study outcome;
- consider factors external to the study when relevant information becomes available, such as scientific or therapeutic developments that may have an impact on the safety of the participants or the ethics of the trial;
- protect the safety of the study participants;
- report on the safety and progress of the trial;
- make recommendations to the NIH, the PI, and the Stanford University Administrative Panel on Human Subjects in Medical Research (Institutional Review Board, IRB) concerning continuation, termination or other modifications of the trial based on the observed beneficial or adverse effects of the treatment under study;
- ensure the confidentiality of the trial data and the results of monitoring; and,
- assist NIH by commenting on any problems with study conduct, enrollment, and sample size and/or data collection.

As an additional safety measure and potential benefit to participants, we will also screen participants for pre-existing or incident conditions that may pose a risk to their health, but are not expected to result from participation in the study. This represents an additional safety mechanism for study participants. Parents/guardians will be notified and referred to their primary medical care provider for further evaluation and care as needed, according to the appropriate current recommended cut-offs for abnormal measures of dyslipidemias, impaired fasting glucose/prediabetes, and diabetes. Notifications and referrals are made in writing, with a full explanation, and followed-up with subsequent phone calls.

d. Study Conclusion

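### Purging is named only as an entry exclusion; no 3- or 6-month measure is stated to ask about it, and new purging without a provider visit would not be systematically recorded as an adverse event.

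*Protocol*

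**What the plan says.** Protocol section 4.c (Vulnerable Populations) raises the issue itself: "Some also express concern that obesity treatment can increase the risk of unhealthful eating behaviors". It adds that most of the data do not support this, and then that "we carefully consider the risks of disordered eating behaviors in all our obesity prevention and treatment research". Section 5.c (Procedures to Minimize Risk) repeats that treatment is not thought to cause disordered eating, but says that "overweight children and families seeking treatment are at increased risk irrespective of participating in treatment".

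The response stated in both places is exclusion at entry. In section 4.c, "any self-induced vomiting, or use of diuretics or laxatives for weight loss are exclusions for the study"; in section 4.g.ii, a household is ineligible if the parent or any child has had an eating disorder diagnosis or "self-induce vomits or uses diuretics or laxatives for weight loss". Section 4.h says the online screener assesses these criteria, and section 2.a says a parent or guardian completes it.

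For follow-up, section 2.a repeats the baseline measures at 3 and 6 months, apart from demographics and a few baseline-only measures that it does not list. The baseline survey domains include eating habits, overconcern with weight or shape, and psychosocial measures.

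Sections 4.c and 5.c both define an adverse event as "any medical illnesses or injuries requiring a visit to a medical care provider or institution". Section 2.g states: "The study will be terminated if there is clear evidence of harm or harmful side-effects of the treatment", where that harm outweighs the evidence of benefit. The SAP contains no safety analysis.

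**The concern.** A harm serious enough to exclude families at entry would normally be asked about again after randomisation. Here the behaviours are named at the door and not afterwards, and the general safety net depends on a visit to a provider. Purging can go on without one.

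What is at stake is the meaning of the safety reports. The Safety Officer recommends continuing or terminating at each report, about every six months. If nobody is asked about purging, a report with no eating-related events cannot separate absence of the behaviour from absence of the question, and there is no systematic count to compare between arms.

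**Working it through.** The plan gives no figure to reproduce. The check sets the relevant text side by side and then works out what asking the question would buy.

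**Where new purging could be picked up after randomisation**

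| Route | Protocol section | Would it record purging without a provider visit? |
|---|---|---|
| Screener items | 4.g.ii, 4.h | No: used once, before enrolment, and answered by the parent |
| Repeated surveys | 2.a | Not stated: domains are listed, items are not; no domain names purging |
| Overconcern with weight or shape | 2.a | No: probably repeated, but it measures an attitude, not a behaviour |
| Adverse event | 4.c, 5.c | No: a visit is part of the definition |
| Serious adverse event | 4.c | No: needs hospitalisation, disability, threat to life or a birth defect |
| Staff recording between visits | 5.c | Not as written: it covers adverse events, so the visit condition still applies, and staff must first become aware |
| Unanticipated problem | 4.c | Possible in principle: no visit condition, but the investigator classifies events already reported, so this is not active ascertainment |

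No route is stated to ask about the behaviour itself at 3 or 6 months.

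**An inconsistency that bears on this**

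Section 4.c assesses, at 3 and 6 months, adverse events that the participant believes may be related to the study. Section 5.c has no such filter and aims to document every adverse event. A child seen by a provider for a new eating problem, whose family does not link it to the study, would be recorded under section 5.c but not under section 4.c. The difference therefore decides which eating-related visits count.

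**What the items would buy**

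Inputs: 80 children per arm (SAP, Detectable Difference, Sample Size, and Power). The upper value is 240/2 = 120 per arm, from the maximum of 240 children in protocol section 4.a, assuming an equal split.

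If no child among n reports the behaviour, the one-sided 95% upper limit on the rate is 1 − 0.05^(1/n), which is approximately 3/n:

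- n = 80: 1 − 0.05^(1/80) = 3.68%; approximation 3/80 = 3.75%.
- n = 120: 1 − 0.05^(1/120) = 2.47%; approximation 3/120 = 2.5%.

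These limits assume every child is followed and children are independent. Attrition lowers n, and siblings (section 4.a allows several children per family) lower the effective n; both raise the limit. The limit applies to self-reported purging. If some children conceal it, the true rate could be higher.

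**The case against.** The strongest reply is that the case rests on surveys the reader cannot see. Eating habits or psychosocial measures could already contain a purging question. That stands: the documents show that no such item is named, not that none exists. A reader might infer that ascertainment is zero in both arms, and the documents do not support that.

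A reader might also infer that all new cases would go unrecorded. They would not. A case that leads to a provider visit is an adverse event under section 5.c (under section 4.c only if believed possibly related), and a hospitalised case is a serious adverse event. Nor is exclusion the only handling of the risk: overconcern is probably repeated, staff are trained to record adverse events between visits, and the unanticipated-problem category needs no visit.

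The section 5.c screen for "abnormal measures of dyslipidemias, impaired fasting glucose/prediabetes, and diabetes" should not be held against the plan. It is for conditions not expected to result from participation, so a suspected treatment harm would not belong in it.

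The protocol also attributes the concern to obesity treatment in general, which both arms receive, and describes the randomised content as directed at well-being rather than specifically at weight. That is a fair reason not to expect a large difference between arms. It does not replace asking, since the protocol supports the benefit of these interventions with studies in other domains such as schools.

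Finally, it is tempting to say that purging would lower BMI and so pass for benefit. The documents give neither an incidence nor an effect on BMI. As an assumption only, 3.75% incidence in one arm and a drop of 1 to 3 kg/m² per case would shift that arm's mean by 0.0375 × 1 = 0.04 to 0.0375 × 3 = 0.11 kg/m², against the SAP's design difference of 0.4 kg/m². Cases in both arms would shrink the net shift. A material effect on the primary result is not established.

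**Conclusion.** The point holds as an inexpensive improvement to safety ascertainment. The protocol excludes households for these behaviours and describes the population as at increased risk, but it states no follow-up question about them. New purging without a provider visit falls outside its adverse event and serious adverse event definitions.

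The size of the gap cannot be given, because the documents contain no rate for the behaviour. What can be given is the information gained by asking: zero reports would bound the self-reported rate per arm at about 3.7% (80 children) to 2.5% (120 children), with complete follow-up and independent children. The conclusion rests on the survey domains as listed. If the sponsor confirms that the instruments already contain the items, what remains is to classify a positive as an event, tabulate it by arm, and settle the adverse event scope. Nothing here calls the primary BMI analysis into question.

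**What to change.** 1. Include the screener items on vomiting and on laxative or diuretic use for weight loss in the 3- and 6-month surveys, or confirm that they are already there. The screener is answered by a parent, so the wording needs adapting for the child survey.
2. Record a new positive as a safety event whether or not a provider was seen.
3. Tabulate these events by arm for the Safety Officer, next to the overconcern measure, with the number of children who answered as the denominator. State whether overconcern is among the baseline-only measures.
4. Reconcile the adverse event scope in sections 4.c and 5.c.
5. Leave the clinical handling of a positive answer to the sponsor, to be written down before the items go live.

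The cost is a protocol amendment, a few added questions on surveys already given, one safety table, and staff time to review positive answers. Because entry status rests on a parent's report, a child's positive at follow-up may predate randomisation. Randomisation supports the comparison between arms, but the count should not be read as purely incident cases.

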5. RISKS

a. Potential Risks

i. Investigational devices

N/A

ii. Investigational drugs

N/A

iii. Commercially available drugs, biologics, reagents or chemicals

N/A

iv. Procedures

Blood tests (venipuncture) are associated with transient local discomfort and possible bruising. Blood draws will occur at baseline and 6-month follow-up assessments. None of our measures have been associated with complications in our recent studies with hundreds of children in this same age group, using the similar measurement protocols.

v. Radioisotopes/radiation-producing machines

N/A

vi. Physical well-being

No evidence of risk to physical well-being.

vii. Psychological well-being

No evidence of risk to psychological well-being. Previous research using similar interventions have enhanced psychological well-being in both children and adults.

viii. Economic well-being

No evidence of risk to economic well-being.

ix. Social well-being

No evidence of risk to social well-being.

A breach of confidentiality might be considered a risk to social well-being, however this has not occurred in our studies to date.

x. Overall evaluation of risk

Low

b. International Research Risk Procedures

N/A

c. Procedures to Minimize Risk

A data collection/tracking system will provide confidentiality to all participants. All collected data are identified by study identification numbers but not names. No one except the research staff will have access to data. Electronic data will be kept in password protected files on password protected computers and all data forms and computers are kept in locked offices, to comply with Stanford Medical Center HIPAA policies. Consistent with Stanford University policy, all project staff will be required to complete the Human Subjects and HIPAA training modules for certification. These methods have proven successful at protecting confidentiality in our prior research.

Adverse events (any medical illnesses or injuries requiring a visit to a medical care provider or institution) will be assessed as part of the follow-up assessments. An adverse events recording form has been designed for this purpose, to systematically document all adverse events occurring during the course of the study (to at least include a brief description, severity, resolution, potential relationship to study participation, and action taken with respect to study participation). Intervention staff will also be trained to investigate and record adverse events continuously, between assessments, as they become aware of them.

Although the evidence suggests treatment does not cause disordered eating, overweight children and families seeking treatment are at increased risk irrespective of participating in treatment. Therefore, as noted above, diagnosis of anorexia nervosa, bulimia nervosa or binge eating disorder, past or present, as well as self-induced vomiting and use of diuretics or laxatives for weight loss are exclusions for the study for both children and parents.

A Safety Officer and the Stanford University Administrative Panel on Human Subjects in Medical Research (IRB) will be informed within 7 days of learning of all unanticipated

problems. With the exception of SAEs for otherwise healthy childbirth, all adverse events, regardless of seriousness, will be reported to the IRB during annual reports/reviews.

The Safety Officer is an independent physician who is designated to provide ongoing oversight to protect participant safety and make ongoing assessments of the balance between risks and benefits. The Safety Officer is a Stanford University faculty member who is not involved in this study or in the Principal Investigator's chain of command. They have relevant clinical and clinical trials experience and expertise. Confidentiality of participant data will be maintained throughout all Safety Officer reviews. The Safety Officer will act in an advisory capacity to NIH, the Principal Investigator, and Stanford University to monitor patient safety and the performance of the study.

Throughout the course of the study, while participants are enrolled, the Safety Officer will meet with the Principal Investigator to review study progress and safety, including all adverse events. An emergency meeting may be called at any time by the Principal Investigator, the Safety Officer or the study Statistician, should questions of participant safety arise. At meetings during the course of the trial, the Safety Officer's responsibilities are to:

- review plans for data safety and monitoring;
- evaluate the progress of the trial, including periodic assessments of data quality and timeliness, participant recruitment, accrual and retention, participant risk versus benefit, and other factors that can affect study outcome;
- consider factors external to the study when relevant information becomes available, such as scientific or therapeutic developments that may have an impact on the safety of the participants or the ethics of the trial;
- protect the safety of the study participants;
- report on the safety and progress of the trial;
- make recommendations to the NIH, the PI, and the Stanford University Administrative Panel on Human Subjects in Medical Research (Institutional Review Board, IRB) concerning continuation, termination or other modifications of the trial based on the observed beneficial or adverse effects of the treatment under study;
- ensure the confidentiality of the trial data and the results of monitoring; and,
- assist NIH by commenting on any problems with study conduct, enrollment, and sample size and/or data collection.

As an additional safety measure and potential benefit to participants, we will also screen participants for pre-existing or incident conditions that may pose a risk to their health, but are not expected to result from participation in the study. This represents an additional safety mechanism for study participants. Parents/guardians will be notified and referred to their primary medical care provider for further evaluation and care as needed, according to the appropriate current recommended cut-offs for abnormal measures of dyslipidemias, impaired fasting glucose/prediabetes, and diabetes. Notifications and referrals are made in writing, with a full explanation, and followed-up with subsequent phone calls.

d. Study Conclusion

The study will be terminated if there is clear evidence of harm or harmful side-effects of the treatment or participation in the study that outweighs evidence of the benefits of participation, if study progress (study accrual, participant retention, ability to implement the study) is judged to be insufficient to result in a valid study, or new information becomes available from other studies suggesting the risks of participation in this study outweigh the potential benefits.

Each Safety Officer report will conclude with a recommendation to continue or to terminate the study. A copy of this letter will be forwarded to the IRB and the NIH Program Officer. A termination recommendation may be made by the Safety Officer at any time during the study if deemed necessary.

We will not perform interim analyses of treatment outcomes or terminate the study early for efficacy or futility, for reasons related to the nature of the research question (see full explanation above). The Safety Officer may make a request for interim analyses at any time during the study for purposes of assessing safety/harm.

e. Data Safety Monitoring Plan (DSMC)

i. Data and/or events subject to review

The database manager and statistician will compile and report: recruitment and retention, quality control of measurements, fidelity of the of intervention implementation, participant progress in the study, and all AE, SAEs, and UPs.

ii. Person(s) responsible for Data and Safety Monitoring

The Principal Investigator and the Co-Investigators have primary responsibility. In addition, we have appointed an independent and qualified Stanford Investigator, [name], as a Safety Officer, who has been approved by the sponsor (NIDDK, NIH).

iii. DSMB Reporting

We will report unexpected deaths or life-threatening experiences related to the research to the IRB within 5 working days from the PD learning of the event. An unanticipated problem (UP) will be reported to the IRB within 10 working days from receiving assessment from the Safety Officer. All other adverse events will be documented monthly and reported to the Safety Officer semi-annually and to the IRB annually.

iv. Will the Protocol Director be the only monitoring entity? (Y/N)

No

v. Will a board, committee, or safety monitor be responsible for study monitoring? (Y/N)

Yes

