In our previous research we have offered similar levels of compensation. Families have told us that financial compensation is not necessary or an important reason for joining the study but they do appreciate this expression that we value their time and participation in the measures. In our experience, these payments do not constitute undue pressure to participate in the study.

k. Costs to Participants

Participants are not charged for participation in the research study.

l. Planned Duration of the Study

Each child and parent/guardian will participate for a total of 6 months.

(i) Screening

Pre-screening online is estimated to take less than 15 minutes.

(ii) Active Participation in the Study

Baseline: Explanation of the study, confirmation of eligibility, completion of the consent/assent, and baseline measures will occur face-to-face via two Zoom calls. Estimated time = 90-120 minutes.

Intervention activities are sent to families by Qualtrics links via REDCap 9 times (throughout the 6 months study). Activities include short videos which range in length from 45 seconds to 5 minutes and/or a Qualtrics reading and writing activity that should take less than 15 minutes.

Follow-up Assessment Appointments: Face-to-face via Zoom follow-up assessments will occur approximately three months and six months after randomization. At the 3 and 6-month assessments, surveys will be administered, diet recalls collected, and height and weight will be measured. After six months, blood test requisitions will also be emailed. Estimated time for the 3- and 6-month Zoom appointments is 60 minutes.

(iii) Analysis of Participant Data

We anticipate keeping this protocol active for at least 10 years (5 years beyond the end of participant involvement) to complete data analysis and paper writing.

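### Serious adverse events not classed as unanticipated problems have only a semi-annual scheduled route to the Safety Officer, a wait of up to about 6 months after staff learn of them

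*Protocol*

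**What the plan says.** The reporting rules are spread over several protocol sections; the SAP does not address them.

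- **Definition and collection.** Section 4.c defines serious adverse events as those involving hospitalisation, lasting or significant disability, threat to life, or a birth defect. They are asked about at two visits: "had any problems that were life-threatening, or resulted in a birth defect in a newborn child) will be assessed at 3 and 6 months". Section 5.c adds collection between visits: "Intervention staff will also be trained to investigate and record adverse events continuously, between assessments".
- **Classification.** Section 4.c: "The PI will evaluate each event to determine if it meets the criteria of an Unanticipated Problem (UP"). The criteria are that the event is unexpected, possibly related to participation, and harmful.
- **Fast routes.** Section 5.c: "A Safety Officer and the Stanford University Administrative Panel on Human Subjects in Medical Research (IRB) will be informed within 7 days" of learning of an unanticipated problem. Section 5.e.iii sends deaths and life-threatening events that are both unexpected and research-related to the IRB within 5 working days.
- **Everything else.** Section 5.e.iii: "All other adverse events will be documented monthly and reported to the Safety Officer semi-annually and to the IRB annually".
- **Cycle and participation.** Section 2.g: "Each Safety Officer report (approximately every six months) will conclude with a recommendation to continue or to terminate the study". Section 4.l: "Each child and parent/guardian will participate for a total of 6 months".
- **Role.** Section 5.c describes the Safety Officer as "designated to provide ongoing oversight to protect participant safety".

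**The concern.** The residual category in section 5.e.iii is defined by what an event is not, and seriousness does not take an event out of it. A hospitalisation, a disabling event, or a life-threatening event judged unrelated falls into the same six-monthly batch as a minor illness.

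The sorting depends on judgements of relatedness and expectedness, and section 4.c gives the evaluation to the PI. Two features of this trial make a timely second look useful. First, section 5.c says that families seeking treatment are at raised risk of disordered eating whether or not they take part. A serious eating-related event could therefore be judged expected or unrelated and so leave the fast route. Second, the investigators are blinded until final follow-up (section 2.a, Randomization), so a PI judging events one at a time cannot see an imbalance between arms. The Safety Officer may ask for an interim analysis of harm or recommend termination at any time (sections 2.g and 5.d), but needs to know of the events to have a reason to do so.

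At stake is how soon someone outside the study team sees a serious event, or a run of them, in a trial of children aged 10 to 16.

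**Working it through.** The plan states no figure to reproduce. The check has two parts: tracing the route, then comparing the clocks.

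**Route of a serious event not classed as an unanticipated problem**

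1. The 7-day notice in section 5.c does not apply, because it covers unanticipated problems only.
2. The 5-working-day route in section 5.e.iii does not apply unless the event is a death or life-threatening, unexpected and research-related. Even then the stated recipient is the IRB.
3. What is left is the residual rule: logged monthly, to the Safety Officer semi-annually, to the IRB annually.

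**Wait after staff learn of the event**

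- Report cycle: about 6 months, or 365.25 / 2 ≈ 183 days (sections 2.g and 5.e.iii).
- Participation: 6 months (section 4.l). Ratio of cycle to participation: 6 / 6 = 1.0.
- Longest wait after learning: about 183 days now, 7 days under the fix.

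**How often the report would come after the child's month 6**

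This needs two assumptions that the documents do not give: event time T is uniform over months 0 to 6, and report dates fall at random relative to each family's start, so that the wait W is uniform over 0 to 6 months. How promptly staff learn of an event is also unknown, so both extremes are shown.

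- *Known at once.* P(T + W > 6) = 0.50. Mean lag from event to report = mean of W = 3.0 months; maximum 6.
- *Learnt only at the month-3 or month-6 visit.* Half the events are learnt at month 3, with P(3 + W > 6) = 0.50. Half are learnt at month 6, and essentially all of those are late. Together: 0.5 × 0.50 + 0.5 × 1 = 0.75. Mean lag = 1.5 + 3.0 = 4.5 months; maximum 3 + 6 = 9.

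A simulation of 2,000,000 draws under the same assumptions gave 0.500 and 0.750, with mean lags of 3.00 and 4.50 months.

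**The same shares with a 7-day rule, taking the full 7 days each time**

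- *Known at once.* Late only if the event falls in the last 7 days: 7 / 183 ≈ 0.04.
- *Learnt only at visits.* 0.5 × 0 + 0.5 × 1 = 0.50. What remains comes from the visit schedule.

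So the share arriving after month 6 falls from 50% to about 4% at one extreme and from 75% to 50% at the other.

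**The case against.** The best case against is that the semi-annual report is not the Safety Officer's only contact with the trial. Section 5.c has the Safety Officer meet the PI during enrolment to go over all adverse events, and lets the PI, the Safety Officer or the statistician call an emergency meeting. Section 5.e.i has the database manager and statistician compile serious events, so someone other than the PI sees them. The intervention is nine sets of short online activities, section 5.a rates overall risk as low, and the sponsor approved the Safety Officer. No passage contradicts the semi-annual rule.

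Much of this stands, and it limits what may be claimed. Three stronger readings are tempting:

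- *That the PI alone decides.* Section 4.c gives the PI the evaluation but does not say alone. Section 5.e.iii mentions a Safety Officer assessment before an unanticipated problem goes to the IRB. What triggers that assessment is not stated, and nothing says that every serious event is sent for it.
- *That the Safety Officer can hear of these events only twice a year.* That describes the scheduled report, not all possible contact.
- *That the delay is 274 days against 7.* The 274 is 91 + 183, counted from randomisation for an event learnt only at month 3. On that clock the fix gives 91 + 7 = 98. The first 91 days belong to the visit schedule, and the continuous recording in section 5.c may shorten them.

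What the objection does not supply is a required prompt notice. The meetings have no stated frequency in section 5.c, emergency meetings are discretionary, and the Safety Officer cannot call one over an event not yet reported.

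**Conclusion.** The concern holds as a gap in the scheduled route. Serious events not classed as unanticipated problems can wait up to about 183 days after staff learn of them before the semi-annual report brings them to the Safety Officer, and no other provision guarantees earlier notice. The maximum wait follows from the stated cycle. The shares of 50% and 75% rest on the uniform-timing assumptions and are illustrative.

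A reader might infer that the harm-termination rule cannot protect families at all. The documents do not support that. The PI and co-investigators have primary monitoring responsibility (section 5.e.ii) and can act sooner, and families randomised later in a cycle may still be enrolled when the report arrives. Nor would the fix ensure review before a given child's exit, since an event learnt only at month 6 will always come after it. The gain is for events learnt earlier and for children still enrolled. It is a cheap improvement of low priority, given the low risk rating.

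**What to change.** In section 5.e.iii:

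- Take serious adverse events, as defined in section 4.c, out of the residual category.
- Send each one to the Safety Officer within 7 days of staff learning of it, with the PI's judgement of relatedness attached.
- Carry over the exception for healthy childbirth that section 5.c already makes for IRB reporting.
- Keep the semi-annual summary for non-serious events.

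At the same time, reconcile the timing for reporting unanticipated problems to the IRB. It is immediate in section 4.c, 7 days from learning in section 5.c, and 10 working days from the Safety Officer's assessment in section 5.e.iii. State also what triggers that assessment.

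The cost is protocol wording, forwarding a small number of forms that already record severity and relationship to the study, and a few extra reviews for the Safety Officer. No new data are collected.
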